PREVENTION OF VENOUS THROMBOEMBOLISM
FOLLOWING RADICAL PROSTATECTOMY

NCT03006562

Date Version Submitted to IRB: 3/18/17

IRB Approval Date of Current Version: 4/4/17

JHM IRB - eForm A – Protocol

- Use the section headings to write the JHM IRB eForm A, inserting the appropriate material in each. If a section is not applicable, leave heading in and insert N/A.
- When submitting JHM IRB eForm A (new or revised), enter the date submitted to the field at the top of JHM IRB eForm A.

Title: A Randomized Controlled Trial for Prevention of Venous Thromboembolism following Radical Prostatectomy

1. Abstract

- a. Provide no more than a one page research abstract briefly stating the problem, the research hypothesis, and the importance of the research.

This research proposal aims to evaluate the PREvention of VENous ThromboEmbolism (VTE) following Radical prostatectomy (RP) for prostate cancer (the PREVENTER trial) by comparing the use of perioperative pharmacologic prophylaxis (subcutaneous heparin) with intermittent pneumatic compression devices (IPCs) to the use of IPCs alone. Currently, there is no standard practice for VTE prophylaxis after RP with the American Urological Association recommending “pharmacological or pneumatic mechanical prophylaxis” for high risk patients. Prior studies showed 30% of patients in the United States received no perioperative prophylaxis and less than 20% received pharmacologic agents, compared to 98% of patients receiving pharmacologic prophylaxis in the United Kingdom. Some urologists prescribe patients low molecular weight heparin (LMWH) after discharge for up to 30 days after surgery. Additionally, there are no established risks of pharmacologic prophylaxis for RP patients, but some urologists express concern about the potential impact of prophylaxis on the rate of postoperative lymphoceles or hematomas. At Johns Hopkins, patients do not routinely receive pharmacologic VTE prophylaxis in the perioperative setting for RP. Given the lack of standard practice and implications for patient safety, we propose a randomized controlled trial to evaluate the impact of perioperative pharmacologic prophylaxis on VTE following RP hypothesizing that it will prevent VTE events without significantly impacting the rate of postoperative bleeding or lymphoceles.

2. Objectives (include all primary and secondary objectives)

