The primary efficacy outcome will be the incidence of symptomatic VTE within 30 days after surgery. A symptomatic VTE event will be defined as any imaging-confirmed VTE diagnosed after evaluation for VTE prompted by the presence of signs/symptoms concerning for VTE. The primary analysis will compare this rate between treatment arms at the 30-day follow-up for all patients. Symptomatic VTE will also include any deaths attributed to a clinically suspected VTE event without imaging confirmation (if autopsy is performed, VTE must be confirmed at autopsy; if autopsy is not performed, clinical suspicion of VTE as the cause will suffice). Symptoms prompting evaluation include:

1. Persistent unilateral or bilateral lower extremity edema
2. Persistent calf pain or cramping
3. Persistent or new chest pain
4. Persistent or new shortness of breath that started suddenly or worsens with exertion
5. Productive cough with bloody sputum
6. Fever and/or tachycardia without any known source of infection
7. Any other clinical concern for DVT or PE

The primary safety outcomes will include three separate measures of incidence of symptomatic lymphocele, incidence of symptomatic hematoma, or major bleeding within 30 days after surgery. Symptomatic lymphocele and symptomatic hematoma will include imaging confirmed events based on imaging pursued at the discretion of the primary attending urologist per routine practice (current routine practice involves imaging only if clinical symptoms suggest possibility of a lymphocele or hematoma). Events will be recorded regardless of the need for intervention (e.g. drain placement by interventional radiology). While screening studies show rates of 25-50% for postoperative lymphocele regardless of surgical approach (open or robotic), the rate of symptomatic lymphocele is thought to be around 10% or less [31,32]. Major bleeding will be defined as the need for transfusion of ≥ 2 units of packed red blood cells after the completion of surgery for anemia attributed to postoperative bleeding or need to return to the operating room for active bleeding.

c. Secondary outcome variables.

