The secondary outcomes (all regarded separately) will be estimated blood loss from surgery, total surgical drain output after surgery (for patients with surgical drains), the overall incidence of VTE (asymptomatic or symptomatic) determined from the subcohort undergoing lower extremity Duplex screening ultrasound, and surveillance bias (measured by use of postoperative diagnostic imaging). Estimated blood loss will be recorded from the anesthesia data report from surgery. Total surgical drain output will be recorded based on ins and outs flowsheets routinely recorded by nurses when emptying drains. Surveillance bias will be determined by recording the type and frequency of postoperative imaging performed while a patient is in the hospital or within 30 days of surgery after discharge.

The overall rate of VTE will only be determined for patients in the subcohort. The asymptomatic VTE will be determined based on the results of the screening lower extremity Duplex ultrasound for asymptomatic DVTs. The overall rate of VTE will be determined by adding the number of asymptomatic VTE events to the number of symptomatic VTE events experienced in the subcohort.

d. Statistical plan including sample size justification and interim data analyses.

Pharmacologic VTE prophylaxis can be expected to prevent between 67% to 75% of DVTs [33]. Given the lowest expected primary outcome event rate will be for VTE, the trial sample size will be based on a power of 80% ($\beta=0.2$) and one-sided α of 0.05 for prevention of post-operative VTE with pharmacologic prophylaxis reducing the rate from 5% to 1.5%. Including two interim analyses of the primary endpoint as outlined in the Interim Analyses section below, the total sample size needed will be 666 (333 per treatment arm) based on 2000 simulations for 82% power (exact α -spending and futility boundaries are outlined below). As mentioned above, the primary efficacy analysis will compare symptomatic VTE rates at the 30-day follow-up for all patients. Secondary analyses will be conducted to compare secondary outcomes between treatment arms at the completion of the study as well. It is expected that during full-time patient enrollment, the study would require about 2 years to accrue patients assuming 50% enrollment.

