Two planned interim analyses of the primary endpoint will be conducted, after one-third and two-thirds of patients have undergone RP. Early stopping for efficacy or futility will be assessed at these time points. Details are provided below under Interim Analyses.

Statistical analyses: The treatment and control groups will be compared to identify any imbalance after randomization in relevant characteristics. Comparisons will include factors such as age, race, BMI, comorbidities, prostate volume, tumor stage, operative time, and blood loss. Discrete factors will be compared with chi-squared test, and continuous factors will be compared with t-test or Wilcoxon ranksum test if data do not conform to a Gaussian distribution. Analysis of the primary outcome (symptomatic VTE) will compare 30 day post-RP rates between the treatment and control groups, using chi-squared test. Logistic regression will be used if adjustment is required for any potential confounders not balanced by randomization, with the treatment effect estimated by the odds ratio and 95% confidence interval. Similar comparison of univariate rates, and adjusted odds ratios will be used for the 3 primary safety endpoints (lymphocele, hematoma, occurrence of major bleeding), and for the secondary outcome of any VTE (restricted to patients who undergo the 30 day lower extremity Duplex ultrasound). Secondary endpoints with a continuous metric (blood loss, surgical drain output, number of imaging tests (surveillance bias)) will be compared in univariate fashion using t-test or Wilcoxon ranksum, and adjusted analyses will use linear regression. Note that analysis of drain output is confined to patients with drains placed, so it is not protected by the randomization, potentially limiting interpretability if the number of patients is small and confounding factors are not well balanced. All analyses of primary and secondary outcomes will be based on intention to treat (ITT). Per protocol analyses will also be conducted, but treatment success will be based on ITT.

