Additional subanalyses (both ITT and per protocol) will be performed with stratification by arm compliance (proportion of scheduled subcutaneous heparin doses administered), performance of pelvic lymphadenectomy (including number of nodes removed), performance of open or robotic surgery (including differences in operative time), and other demographic and comorbidity criteria (including history of VTE, cancer, and other risk factors included in the Caprini Score) to identify patients at highest risk for VTE. Surveillance bias will also be evaluated, as mentioned above, by the differential performance of diagnostic imaging.

e. Interim Analyses.

Two interim analyses of the primary endpoint are planned with potential early stopping for efficacy or futility. O'Brien-Fleming boundaries were used, as implemented in PASS v. 11 (NCSS Software, Inc., Kaysville, UT). The total sample size needed for 82% power with a 1-sided test is 666 (333 per treatment arm), based on 2000 simulations. The interim analyses will be conducted after 1/3 and 2/3 of patients are enrolled (222 and 444, respectively). Alpha-spending at the 2 interim analyses and final analysis is .001,

.015, and .033 (cumulative alpha spent .001, .015, .048), respectively. The futility boundaries at the 1st and 2nd interim analyses, and final analysis are $p=0.816$, 0.272 , and 0.070 , respectively.

At each interim analysis the rates of the 3 safety endpoints (lymphocele, major bleeding, and hematoma) will also be evaluated and 95% confidence intervals calculated. Unacceptable rates for these endpoints are $\geq 15\%$, $\geq 5\%$, and $\geq 10\%$, respectively. If lower 95% confidence bounds meet or exceed these unacceptable rates the trial will be halted for further review and consideration of early stopping.

8. Risks

- a. Medical risks, listing all procedures, their major and minor risks and expected frequency.

Administration of subcutaneous heparin:

1. Major risks:

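### Do the three primary safety outcomes need a stated margin, sidedness and power, and must the interim safety rule say whether its rates are by arm or pooled?

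*Combined protocol and SAP*

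**What the plan says.** The Abstract (Section 1) states a two-part hypothesis about heparin, "hypothesizing that it will prevent VTE events without significantly impacting the rate of postoperative bleeding or lymphoceles". Section 2 lists lymphocele, hematoma and major bleeding as primary safety outcomes, each framed as a question of whether heparin increases it.

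Section 7d sets the sample size from VTE only: "Given the lowest expected primary outcome event rate will be for VTE, the trial sample size will be based on a power of 80" per cent, with a one-sided alpha of 0.05, for "prevention of post-operative VTE with pharmacologic prophylaxis reducing the rate from 5% to 1.5" per cent. That gives 666 patients, 333 per arm, with 82% power after two interim analyses.

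For the final safety analysis Section 7d says: "Similar comparison of univariate rates, and adjusted odds ratios will be used for the 3 primary safety endpoints". The sentence before it describes the VTE analysis, with a chi-squared test and, where adjustment is needed, logistic regression "with the treatment effect estimated by the odds ratio and 95% confidence interval". The only expected safety rate in the plan is in Section 7b: "the rate of symptomatic lymphocele is thought to be around 10% or less".

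Section 7e adds an interim check: "At each interim analysis the rates of the 3 safety endpoints (lymphocele, major bleeding, and hematoma) will also be evaluated", with 95% confidence intervals. "Unacceptable rates for these endpoints are" 15% or more for lymphocele, 5% or more for major bleeding and 10% or more for hematoma. If a lower 95% bound reaches its limit, the trial pauses for review. Section 4c says that data analysis is blinded to treatment group.

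**The concern.** Three outcomes are labelled primary and carry half of the trial's hypothesis, yet every design parameter belongs to VTE. A reader could fear two things.

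First, a non-significant safety comparison might be reported as showing no harm when the trial had little chance of detecting a moderate increase. Sizing on the outcome with the lowest expected rate does not guarantee power for the others: for a fixed absolute increase, power falls as the base rate rises.

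Second, the interim rule speaks of rates without saying whose. If a blinded analyst pooled the arms, harm confined to the heparin arm would be averaged with the control arm, and the rule would seldom trigger. At stake would be the safety conclusion and the trial's main numerical safeguard.

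**Working it through.** **Inputs.** From Section 7d: 333 per arm; VTE 5% and 1.5%; one-sided alpha 0.05. From Section 7b: lymphocele about 10% or less. From Section 7e: looks at 222 and 444 patients (taken as 111 and 222 per arm); limits of 15%, 5% and 10%. The plan gives no expected rate for bleeding or hematoma, so those control rates are assumptions.

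**1. The plan's own figure.** For the pooled z-test (equivalent to chi-squared), power ≈ Φ[(|p1 − p0| − z·s0)/s1], where s0 = √(2p̄(1 − p̄)/n), s1 = √((p0(1 − p0) + p1(1 − p1))/n) and p̄ is the mean of the two rates. For VTE, p̄ = 0.0325, s0 = 0.01374 and s1 = 0.01368. Then (0.035 − 1.645 × 0.01374)/0.01368 = 0.906, and Φ(0.906) = 81.8%. Simulating the group-sequential design, with 0.001, 0.015 and 0.048 as nominal p-values and the interim futility limits applied, gives 82.4%. The stated 82% is reproduced.

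**2. Power for harm at 333 per arm.** By the same formula, lymphocele 10% to 15% at two-sided 0.05 has s0 = 0.02563 and s1 = 0.02556. Then (0.05 − 1.96 × 0.02563)/0.02556 = −0.009, and Φ(−0.009) = 49.6%. Exact binomial enumeration of the same test gives:

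| Outcome | Control → heparin | Two-sided 0.05 | One-sided 0.05 |
|---|---|---|---|
| Lymphocele | 7% → 15% | 92% | 96% |
| Lymphocele | 8% → 15% | 81% | 89% |
| Lymphocele | 9% → 15% | 67% | 78% |
| Lymphocele | 10% → 15% | 50% | 62% |
| Lymphocele | 10% → 20% | 96% | 98% |
| Bleeding (assumed control) | 1% → 5% | 90% | 94% |
| Bleeding (assumed control) | 2% → 5% | 57% | 69% |
| Bleeding (assumed control) | 3% → 5% | 26% | 38% |
| Hematoma (assumed control) | 3% → 10% | 97% | 98% |
| Hematoma (assumed control) | 5% → 10% | 70% | 80% |

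The targets in these rows are reviewer's choices. Apart from the 20%, they borrow the interim limits, which the plan does not describe as differences to detect.

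**3. Precision.** If lymphocele is truly 10% in both arms, the half-width of a 95% interval for the risk difference is about 1.96 × √(2 × 0.10 × 0.90/333) = 4.6 points. At 7% in both arms it is 1.96 × √(2 × 0.07 × 0.93/333) = 3.9 points. An interval therefore shows directly which increases remain possible.

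**4. The sizing rationale.** On a relative scale, power rises with the base rate: a doubling has 33% two-sided power from 2%, 70% from 5% and 96% from 10%. On an absolute scale it falls: a 3.5-point difference has 75% at 1.5% against 5%, 36% at 7% against 10.5% and 29% at 10% against 13.5%. The plan's effect measure is the odds ratio, which is relative, and the plan does not claim equal power for equal absolute increases.

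Nor is a conflict with the 5% bleeding limit established. It would arise only if the lowest expected rate means the 5% control VTE rate. Against the 1.5% heparin rate, expected bleeding need only exceed 1.5%. The documents do not say which is meant.

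**5. The interim rule, by arm and pooled.** With a two-sided Clopper-Pearson 95% interval (the plan does not name one), the heparin arm triggers at 11/111 or 19/222 for bleeding, 25/111 or 45/222 for lymphocele, and 19/111 or 32/222 for hematoma. Pooled, the counts are 19/222 or 33/444, 45/222 or 83/444, and 32/222 or 58/444. Chance of halting by the second look, with illustrative true rates:

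| Heparin against control | Heparin arm alone | Pooled |
|---|---|---|
| Bleeding 6% against 2% | 11% | 0.2% |
| Bleeding 8% against 2% | 47% | 3% |
| Bleeding 10% against 2% | 82% | 15% |
| Lymphocele 20% against 10% | 53% | 3% |
| Hematoma 15% against 5% | 64% | 3% |

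When the true rate sits exactly at a limit, the by-arm rule halts only 3% to 4% of the time. The two readings differ most under large harms.

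**6. Which reading the text supports.** Section 7e applies efficacy and futility boundaries to VTE at the same two looks, which needs a between-arm comparison. The data are therefore already split by arm when the safety rates are computed. Blinding under Section 4c is met by coded arm labels and does not require pooling.

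**The case for a change.** The best case for a change is that it costs a few sentences and no patients. The outcomes are primary, lymphocele near 10% lies within the plan's own expectation, and there a rise to the plan's own limit would be missed half the time. The only sidedness stated anywhere is one-sided, and the safety analysis is described as similar to the one it belongs to. That choice alone moves power for lymphocele 10% to 15% from 50% to 62%. Two readers could also run very different interim rules from one sentence.

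Part of this stands. Non-significance alone would not exclude a moderate increase if control rates are near the upper end, and a pooled interim rule would be weak.

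Neither consequence follows from what is written. The one-sided alpha is attached expressly to preventing VTE. A chi-squared test with 95% intervals is ordinarily two-sided, and the safety aims ask whether harm increases, which is a question of detection and not a non-inferiority claim. Nothing says that p above 0.05 will be reported as safety; the Abstract's wording is a hypothesis and not a decision rule. Pooling is a strained reading when the arms are already separated at the same looks, and a trigger leads to review and not to automatic stopping.

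**Conclusion.** No change follows. The plan leaves out detail that analysts will fill sensibly: two-sided safety comparisons, odds ratios reported with 95% intervals, and interim rates for each coded arm. Spelling these out would correct no stated figure and would leave the sample size and the efficacy test as they are. Any increase to be excluded would still be for the sponsor to set.

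The point is a caution for reading the results. At 333 per arm the trial is informative against large harm (lymphocele 10% to 20%, 96% power) and against a rise to 15% from a control rate of 7% or 8% (92% and 81%). It is not informative against a rise to 15% from 10% (50%). With a control rate near 10%, the lymphocele conclusion should rest on the interval, which would extend about 4.6 points either side of the observed difference.

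This rests on the by-arm and two-sided readings, on full enrolment without loss, and, for bleeding and hematoma, on assumed control rates.

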Specific aims: Does the use of perioperative pharmacologic agents (subcutaneous heparin; 5,000 units given before surgery and every 8 hours after surgery until discharge), compared to IPCs alone, for RP for prostate cancer:

1. Prevent the occurrence of symptomatic VTE following surgery? (primary efficacy outcome)
2. Increase the incidence of clinically significant lymphocele? (primary safety outcome)
3. Increase the incidence of clinically significant hematoma? (primary safety outcome)
4. Increase the incidence of major bleeding following surgery? (primary safety outcome)
5. Prevent the occurrence of any VTE (asymptomatic or symptomatic) following surgery? (secondary outcome)
6. Increase estimated blood loss during surgery? (secondary outcome)
7. Increase surgical drain output after surgery? (secondary outcome)

8. Lead to potential surveillance bias measured by increased or decreased use of diagnostic imaging for VTE relative to symptoms (e.g. lower extremity Duplex ultrasound, spiral CT angiography, V/Q scan, etc.)? (secondary outcome)

3. Background (briefly describe pre-clinical and clinical data, current experience with procedures, drug or device, and any other relevant information to justify the research)

An estimated 180,000 new cases of prostate cancer were diagnosed in 2016, and about 90,000 radical prostatectomies are performed in the United States annually [1-3]. Since the year 2000, a sharp change in practice patterns has shifted the traditionally open radical prostatectomy (RP) procedure to current practice where the great majority (likely >70%) are robotic-assisted laparoscopic RPs (RALRP) [3]. According to most guidelines, undergoing RP by any approach classifies a patient as high-risk for venous thromboembolism (VTE), including deep venous thrombosis (DVT) and pulmonary embolism (PE), and would lead to implementation of appropriate intermittent mechanical pneumatic compression devices (IPCs) and pharmacologic prophylaxis [4-8].

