Patients randomized to the pharmacologic VTE prophylaxis arm will receive a dose of subcutaneous heparin 5,000 units within 2 hours prior to incision, and subcutaneous heparin 5,000 units every 8 hours after surgery until discharge. Total number of doses received and missed doses will be recorded. No post-discharge pharmacologic prophylaxis will be prescribed. Per routine care, patients will be requested to inform their urologist's office if they experience any symptoms of DVT or PE, or any other concerns, during the first 30 days after surgery. All patients will receive a phone call around 30 days after surgery to assess primary outcomes including documentation of whether they experienced a postoperative VTE episode and any treatment initiated for confirmed VTE. Any patient endorsing symptoms concerning for VTE up to 30 days after surgery will be recommended to undergo urgent evaluation and care, locally or at Johns Hopkins, with imaging/evaluation results forwarded to Johns Hopkins. Patients and their insurance will be responsible for the costs as part of routine care. The 30-day phone call will be the only planned, study-initiated contact after surgery with the patient to evaluate symptomatic outcomes and will be the same for both the control and pharmacologic prophylaxis arms.

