Urologists will initially be blinded to patient randomization and the administration of the preoperative subcutaneous heparin dose to prevent bias on recorded estimated blood loss during the surgery. Postoperatively, administration of subcutaneous heparin will be unblinded during the patient's inpatient stay. Control patients will receive IPCs only and no placebo doses will be administered during their hospital stay. Data analysis will be blinded as to treatment group. Performance and interpretation of lower extremity Duplex screening ultrasound will be blinded to patient randomization. Surveillance bias will be assessed by differential performance of postoperative imaging as described above.

- d. Justification of why participants will not receive routine care or will have current therapy stopped.

All patients will receive routine care. Both arms include patients receiving accepted standards of care.

- e. Justification for inclusion of a placebo or non-treatment group.

The control group in this trial is the group receiving current routine practice at Johns Hopkins with IPCs. The experimental group is the group receiving pharmacologic VTE prophylaxis as practiced at other centers and recommended by most VTE guidelines for major surgery.

- f. Definition of treatment failure or participant removal criteria.

Participants will be removed from the trial if surgery is canceled or not completed for any reason. All patients assigned to the experimental and control arms completing surgery will be included in the study regardless of compliance with pharmacologic prophylaxis doses in an intention-to-treat (ITT) analysis. Patients experiencing an adverse event will be provided appropriate care. Additional per-protocol analyses will be conducted to compare outcomes by compliance with assigned regimen. Patients diagnosed with VTE events will be recommended to obtain routine care locally or at Johns Hopkins per patient preference.

- g. Description of what happens to participants receiving therapy when study ends or if a participant's participation in the study ends prematurely.

Perioperative pharmacologic prophylaxis is only given during the patient's inpatient stay. As mentioned above, all patients will be included in an ITT analysis as possible if they undergo surgery. No planned outcomes will be tracked after the 30-day post-surgical outcomes unless the patient initiates contact.

5. Inclusion/Exclusion Criteria

Inclusion:

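### Blood loss and operative time arise after the pre-incision heparin dose, yet their imbalance can trigger adjustment of the safety odds ratios, and no rule says whether crude or adjusted governs

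*Combined protocol and SAP*

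**What the plan says.** All references are to the combined protocol and SAP.

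- **Timing of treatment.** Section 4a has the heparin arm receive "subcutaneous heparin 5,000 units within 2 hours prior to incision". Section 6a gives a different window, within 3 hours. The two must be reconciled, but both are before incision, so this point is unaffected.
- **Blood loss as an outcome.** Section 2 (aim 6) asks whether heparin increases it, and section 7c takes it from the anesthesia record of the operation. Section 4c blinds urologists to the preoperative dose "to prevent bias on recorded estimated blood loss during the surgery".
- **Blood loss as an imbalance factor.** Section 7d compares the arms after randomization: "Comparisons will include factors such as age, race, BMI, comorbidities, prostate volume, tumor stage, operative time, and blood loss".
- **Trigger for adjustment.** Section 7d continues: "Logistic regression will be used if adjustment is required for any potential confounders not balanced by randomization". It gives no threshold and no fixed covariate list.
- **Reach.** "Similar comparison of univariate rates, and adjusted odds ratios will be used for the 3 primary safety endpoints". The same paragraph also analyses blood loss as a secondary endpoint.
- **Precedence.** The only ranking stated is "Per protocol analyses will also be conducted, but treatment success will be based on ITT". It orders intention-to-treat against per-protocol, and says nothing on crude against adjusted.

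**The concern.** A confounder must precede treatment. Blood loss and operative time follow the first dose, and the trial itself treats blood loss as something heparin may change. Section 7d therefore gives one variable two roles: an effect of treatment, and a candidate explanation for differences between the arms.

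If heparin raises blood loss, and blood loss goes with postoperative bleeding or hematoma, conditioning on it removes part of the treatment effect. The safety odds ratio then typically moves toward no harm. The trigger makes this worse, because a real heparin effect on blood loss is exactly what produces the imbalance. The final report could hold a significant crude and a non-significant adjusted result for a primary safety outcome, with no prespecified rule for choosing between them. The abstract hypothesizes no significant effect on bleeding or lymphoceles, so the distortion would favour the trial's own hypothesis.

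**Working it through.** **Inputs from the documents.** 333 per arm (section 7d); eight named imbalance factors, of which two are post-dose (7d); 4 to 7 expected heparin doses (section 11), of which one precedes surgery (4a).

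**The plan's own figure.** The plan gives no figure on this point. Its stated 82% power is not in dispute and reproduces closely as a fixed design. For 5% v 1.5%, one-sided 0.05, pooled rate 0.0325:

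- null SE = √(2 × 0.0325 × 0.9675 / 333) = 0.01374
- alternative SE = √((0.05 × 0.95 + 0.015 × 0.985) / 333) = 0.01368
- power = Φ((0.035 − 1.645 × 0.01374) / 0.01368) = 81.8%

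**Assumptions (none from the documents).** The imbalance flag is a two-sided t-test at 0.05. Blood loss is standard normal in controls and shifted by d SD on heparin. The log-odds of the safety event rise by g per SD of blood loss. Control risks of 10% and 5% echo the symptomatic lymphocele rate in 7b and the unacceptable major bleeding rate in 7e.

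**Step 1: how often the flag fires.** The noncentrality is d × √(333/2) = 12.90d.

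| d (SD) | Noncentrality | Chance of flag |
|---|---|---|
| 0.1 | 1.29 | 25% |
| 0.2 | 2.58 | 73% |
| 0.3 | 3.87 | 97% |

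**Step 2: total against adjusted odds ratio.** Solve the intercept for the control risk, then average the logistic risk over the heparin-arm distribution of blood loss. Example with 10% control risk, g = 1.0, d = 0.3 and direct OR 1.5: the heparin-arm risk is 17.25%, so the total OR is (0.1725/0.8275) / (0.10/0.90) = 1.88. The model that includes blood loss returns the direct OR (simulated medians 1.49 to 1.53).

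**Step 3: effect on the reported result.** 3,000 simulated trials per row, direct OR 1.5, significance meaning Wald z > 1.96 toward harm. Discordant means crude significant, flag fires, adjusted not significant.

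| Control risk | g | d | Total OR | Crude significant | Adjusted significant | Discordant |
|---|---|---|---|---|---|---|
| 10% | 0.5 | 0.2 | 1.63 | 53% | 38% | 14% |
| 10% | 0.5 | 0.3 | 1.72 | 64% | 39% | 25% |
| 10% | 1.0 | 0.2 | 1.72 | 65% | 36% | 24–27% |
| 10% | 1.0 | 0.3 | 1.88 | 77% | 35% | 42% |
| 5% | 1.0 | 0.2 | 1.76 | 42% | 22% | 18% |
| 5% | 1.0 | 0.3 | 1.92 | 57% | 24% | 33% |

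Repeat runs moved individual cells by up to about 3 points; the range in the third row spans two runs.

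**Step 4: milder and different cases.**

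- 5% risk with g = 0.5: discordance about 9–10% (0.2 SD) and 17–19% (0.3 SD).
- 0.1 SD shift: about 2–8% across both risks and slopes.
- No effect on blood loss: below 1%, and no understatement of the odds ratio.
- Direct OR 2.0: 6–27%.
- All harm through blood loss (d of 0.2 to 0.3, g = 1.0): OR 1.20–1.32 falls to about 1.0, but crude power is only 8–19%. Partial mediation is the more realistic case, since only one dose precedes surgery.
- Unmeasured surgical difficulty driving both blood loss and bleeding (one scenario: 3% risk, 0.3 SD shift, direct OR 1.5): crude 1.74, adjusted 1.30. The adjusted value then falls below even the direct effect.

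**The case against.** The strongest reply is that the plan never proposes the harmful step. The list belongs to a sentence about comparing the arms. Adjustment comes later, under the term confounders, and a variable affected by treatment is not a confounder. The wording for the safety endpoints can also be read as carrying over the efficacy order: crude comparison always, regression only if needed. A careful analyst could read it that way. But the text names blood loss among the factors screened, requires no such reading, and does not say which safety result governs.

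Four further points have weight.

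- The 42% needs the largest shift, the steepest slope and 10% risk together, and every discordance figure assumes that the analyst adjusts whenever the flag fires. The milder cells are therefore shown above.
- The plan sets no significance rule for safety at the final analysis, so crossing 0.05 illustrates a change of reading and not a formal decision. The shift in the odds ratio does not depend on it.
- The halting rule in 7e uses rates without covariates. If it is applied to the heparin arm with exact limits (7e states neither), the two 5%-risk rows would trigger review of major bleeding by the second look in about 56–70% of trials. That is a real backstop during the trial, but it does not protect the final safety estimate.
- The documents suggest no heparin effect on operative time and no blood-loss route to lymphocele. The case is strongest for blood loss as a covariate for bleeding and hematoma.

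**Conclusion.** The concern holds, and the passage is wrong as written: section 7d puts a declared outcome of treatment on the list of factors whose imbalance can lead to adjustment. It should be fixed. The reading of the text is secure. The size of the distortion is conditional: it requires that heparin raise blood loss, that blood loss predict the safety event or share causes with it, and that the analyst adjust for it. With a direct OR of 1.5, shifts of 0.2 to 0.3 SD and the risks and slopes tabulated, total odds ratios of 1.63 to 1.92 shrink to about 1.5, with 14–42% of trials discordant. Outside those settings the discordance can be well under 10%. No size is claimed for operative time.

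For symptomatic VTE the concern is smaller, because the chi-squared comparison is named without condition. Sample size, power and the interim halting rule are unaffected.

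**What to change.** In section 7d:

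1. Remove operative time and blood loss from the imbalance list. Report blood loss as the secondary outcome it already is, and operative time descriptively.
2. State that any adjusted model, for efficacy or safety, uses only prespecified variables measured before the first dose, and that these are not selected by balance tests. Assuming independence and a 0.05 threshold, the six remaining listed factors would flag at least one by chance with probability 1 − 0.95⁶ = 26%.
3. For each safety endpoint, name the governing analysis: the crude comparison, or one adjusted only for the two randomization strata. Label all other adjusted odds ratios as sensitivity analyses.

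This is wording only and needs no new data or patients. The one cost is that a chance imbalance in a pre-dose factor that was not listed could be addressed only in a sensitivity analysis.
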